### **Events NOT Meeting the AE Definition**

- Any clinically significant abnormal laboratory findings or other abnormal safety assessments that are associated with the underlying disease, unless judged by the investigator to be more severe than expected for the participant's condition.
- Medical or surgical procedure (e.g., endoscopy, appendectomy): the condition that leads to the procedure is the AE.
- Situations in which an untoward medical occurrence did not occur (social and/or convenience admission to a hospital, admission for routine examination.).

- Anticipated day-to-day fluctuations of pre-existing disease(s) or condition(s) present or detected at the start of the study that do not worsen. Pre-existing diseases will be recorded in the medical history section of the eCRF.
- Hospitalization for elective treatment of a pre-existing condition (known or diagnosed before signing the informed consent) that did not worsen from baseline.

# 10.3.2. Definition of SAE

An SAE is defined as any untoward medical occurrence that, at any dose, meets one or more of the criteria listed:

- a. Results in death
- b. Is life threatening

The term 'life-threatening' in the definition of 'serious' refers to an event in which the participant was at risk of death at the time of the event. It does not refer to an event, which hypothetically might have caused death, if it were more severe.

- c. Requires inpatient hospitalization or prolongation of existing hospitalization
- In general, hospitalization signifies that the participant has been admitted (usually involving at least an overnight stay) at the hospital or emergency ward for observation and/or treatment that would not have been appropriate in the physician's office or outpatient setting. Complications that occur during hospitalization are AE. If a complication prolongs hospitalization or fulfills any other serious criteria, the event is serious. When in doubt as to whether "hospitalization" occurred or was necessary, the AE should be considered serious.
- Hospitalization for elective treatment of a pre-existing condition that did not worsen from baseline is not considered an AE.
- d. Results in persistent or significant disability/incapacity
- The term disability means a substantial disruption of a person's ability to conduct normal life functions.
- This definition is not intended to include experiences of relatively minor medical significance such as uncomplicated headache, nausea, vomiting, diarrhea, influenza, and accidental trauma (e.g., sprained ankle) that may interfere with or prevent everyday life functions but do not constitute a substantial disruption.
- e. Is a congenital anomaly/birth defect in the offspring of a study participant
- f. Abnormal pregnancy outcomes (e.g., spontaneous abortion, fetal death, stillbirth, congenital anomalies, ectopic pregnancy)
- g. Other situations:
- Possible Hy's Law case: ALT ≥ 3x ULN AND total bilirubin ≥ 2x ULN (>35% direct bilirubin) or INR >1.5 must be reported as SAE

- Medical or scientific judgment should be exercised by the investigator in deciding whether SAE reporting is appropriate in other situations such as significant medical events that may jeopardize the participant or may require medical or surgical intervention to prevent one of the other outcomes listed in the above definition. These events should usually be considered serious.
  - Examples of such events include invasive or malignant cancers, intensive treatment for allergic bronchospasm, blood dyscrasias, convulsions, or development of intervention dependency or intervention abuse.

### 10.3.3. Solicited events

### • Definition of solicited event

• Solicited events are predefined events administration site events and systemic events for which the participant is specifically questioned, and which are noted by the participant in their eDiary.

#### a. Solicited administration site events

The following administration site events will be solicited:

### Table 21 Solicited administration site events

Pain at administration site		
Redness at administration site		
Swelling at administration site		
Lymphadenopathy		
(Axillary swelling/ tenderness ipsilateral to the site of injection)		

### b. Solicited systemic events

The following systemic events will be solicited:

### Table 22 Solicited systemic events

Fever
Headache
Myalgia (muscle pain)
Arthralgia (joint pain)
Fatigue (tiredness)
Chills
Abdominal pain
Vomiting
Diarrhea

Note: Participants will be instructed to measure and record the oral temperature in the evening. If additional temperature measurements are taken at other times of the day, participants will be instructed to record the highest temperature in the eDiary.

### 10.3.4. Unsolicited AE

### **Definition of unsolicited AE**

- An unsolicited AE is an AE that was either not included in the list of solicited events or could be included in the list of solicited events but with an onset outside the specified period of follow-up for solicited events. Unsolicited AEs must have been communicated by participants who signed the informed consent. Unsolicited AEs include both serious and nonserious AEs.
- Potential unsolicited AEs may be medically attended (i.e., symptoms or illnesses requiring a hospitalization, emergency room visit, or visit to/by a healthcare provider). The participants will be instructed to contact the site as soon as possible to report medically attended event(s), as well as any events that, though not medically attended, are of participant concern. Detailed information about reported unsolicited AEs will be collected by qualified site personnel and documented in the participant's records.
- Unsolicited AEs that are not medically attended nor perceived as a concern by the participant will be collected during an interview with the participants and by review of available medical records at the next visit.

# 10.3.5. Recording, assessment and follow-up of AE, SAE, AESIs and pregnancies

### 10.3.5.1. AE, SAE and AESI recording

- When an AE/SAE/AESI occurs, it is the responsibility of the investigator to review all documentation (e.g., hospital progress notes, laboratory reports, and diagnostics reports) related to the event.
- The investigator will then record all relevant AE/SAE/AESI information.
- It is not acceptable for the investigator to send photocopies of the participant's medical records to CRO in lieu of completion of the eCRF/required form.
- There may be instances when copies of medical records for certain cases are requested by CRO. In this case, all participant identifiers, with the exception of the participant number, will be redacted on the copies of the medical records before submission to CRO.
- The investigator will attempt to establish a diagnosis of the event based on signs, symptoms, and/or other clinical information. Whenever possible, the diagnosis (not the individual signs/symptoms) will be documented as the AE/SAE.
- An eDiary will be used in this study to capture solicited administration site or systemic events. The participant should be trained on how and when to complete the eDiary.
- Anyone who measures administration site or systemic events and who will record the event in the eDiary should be trained on using the eDiary. This training must be documented in the participant's source record.

- For each solicited and unsolicited AE the participant experiences, the participant will be asked if they received medical attention (defined as unscheduled visit to or from medical personnel for any reason, including emergency room visits). This information will be recorded in the participant's eDiary (for solicited AEs) and in the participant's eCRF as part of normal AE reporting (for unsolicited AEs). If the collection of solicited AEs was not possible for any reasons via the eDiary and solicited AEs were reported to the investigator by the participant, then it would be possible for it to be reported directly to the site staff and submitted (e.g. via the eCRF). Medical attention received for SAEs/AESIs will have to be reported using the normal AE reporting process in the eCRF.
- Any unreturned eDiary will be sought from the participant through telephone call(s) or any other convenient procedure.

## 10.3.5.2. Assessment of intensity

The investigator will make an assessment of intensity for each AE, AESI and SAE reported during the study and assign it to one of the following categories:

• Mild:

A type of AE that is usually transient and may require only minimal treatment or therapeutic intervention. The event does not generally interfere with usual activities of daily living.

• Moderate:

A type of AE that is usually alleviated with additional specific therapeutic intervention. The event interferes with usual activities of daily living, causing discomfort but poses no significant or permanent risk of harm to the research participant.

• Severe:

A type of AE that interrupts usual activities of daily living, or significantly affects clinical status, or may require intensive therapeutic intervention.

The intensity of the following solicited AEs will be assessed as described:

### 219112 (MRNA CLINRES-001) Protocol Amendment 3 Final

# Table 23 Intensity scales for solicited events

Event	Intensity grade	Parameter
Pain at administration site	0	None
	1	Mild: Any pain neither interfering with nor preventing normal
	2	Moderate: Painful when limb is moved and interferes with
	3	Severe: Significant pain at rest. Prevents normal everyday
Redness at administration site	0	Greatest surface diameter < 25 mm
	1	Greatest surface diameter 25 - 50 mm
	2	Greatest surface diameter 51 - 100 mm
	3	Greatest surface diameter > 100 mm
Swelling at administration site	0	Greatest surface diameter < 25 mm
	1	Greatest surface diameter 25 - 50 mm
	2	Greatest surface diameter 51 - 100 mm
	3	Greatest surface diameter > 100 mm
Temperature*	0	< 38.0°C (100.4°F)
	1	38.0°C (100.4°F) - 38.4°C (101.1°F)
	2	38.5°C (101.2°F) - 38.9°C (102.0°F)
	3	>38.9°C (102.0°F)
Arthralgia (joint pain)	0	None
	1	Mild: Arthralgia present but does not interfere with activity
	2	Moderate: Arthralgia that interferes with normal activity
	3	Severe: Arthralgia that prevents normal activity
Headache	0	None
	1	Mild: Headache that is easily tolerated
	2	Moderate: Headache that interferes with normal activity
	3	Severe: Headache that prevents normal activity
Fatigue (tiredness)	0	None
	1	Mild: Fatigue that is easily tolerated
	2	Moderate: Fatigue that interferes with normal activity
	3	Severe: Fatigue that prevents normal activity
Lymphadenopathy	0	None
	1	Mild: No interference with activity
	2	Moderate: Some interference with daily activity or requires
	_	repeated use of non-narcotic pain reliever
	3	Severe: Prevents daily activity or requires use of narcotic pain reliever
Chills	0	None
	1	Mild sensation of cold; shivering; chattering of teeth
	2	Moderate tremor of the entire body; narcotics indicated
	3	Severe or prolonged, not responsive to narcotics
Myalgia (muscle pain)	0	None
	1	Mild: Myalgia present but does not interfere with activity
	2	Moderate: Myalgia that interferes with normal activity
	3	Severe: Myalgia that prevents normal activity
Abdominal pain	0	Normal
	1	Mild: No interference with daily activity
	2	Moderate: Interferes with daily activity
	3	Severe: Prevents daily activity

Event	Intensity grade	Parameter
Vomiting	0	None
	1	Mild: No interference with activity or 1-2 episodes/24 hours
	2	Moderate: Some interference with activity or >2 episodes in 24
	2	hours
	2	Severe: Prevents daily activity, requires outpatient intravenous
	5	hydration
Diarrhea	0	None
	1	Mild: 2-3 loose stools or <400g in 24 hours
	2	Moderate: 4-5 stools or 400-800 g in 24 hours
	2	Severe: 6 or more water stools or >800g in 24 hours
	3	or requires outpatient intravenous hydration

\* Refer to the SoA (Section 1.3) for the definition of fever and the preferred location for temperature measurement.

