### 8.3.7.3. Study holding rules

The safety holding rules are defined in the Table 12. Holding rules 1a-d will be assessed by the investigator on a continuous basis. Meeting any of these holding rules will trigger a hold of study intervention administration irrespective of number of participants enrolled and/or timing of the event. Holding rules 2a-c will be assessed by the iSRC during the safety evaluations on unblinded data.

These holding rules have been written under the assumption that the safety data from all participants will be available. If the data from all participants are not available (i.e., in case a participant is lost to follow-up), then the holding rules will be assessed on a prorata basis (expressed as percentage of participants to be evaluated) i.e., 3 out of 6 sentinel participants or 30% of all participants, whichever is met earlier.

Of note, no formal holding rules will be applied for other safety data such as non-lifethreatening SAEs, missed visits due to study intervention related AEs, Grade 1 and Grade 2 solicited and unsolicited AEs in the 7-day follow-up period (Day 1 to Day 7) and unsolicited AEs collected from Day 8 to Day 31 after study intervention administration. However, if available, these data will also be reviewed by the iSRC to allow an overall assessment of the benefit/risk ratio of study intervention administration.

Holding rule	Event (per dose and per individual study group)	Number of participants to pause vaccination in all groups, pending further evaluation by iSRC
1a	Death or any life-threatening SAE regardless of causality	≥1
1b	Any non-life-threatening SAE that cannot be reasonably attributed to a cause other than vaccination as per investigator or sponsor assessment	≥1
1c	Any withdrawal from the study (by investigator or participant request) following a Grade 3 AE	≥1
1d	Any administration site or systemic solicited AE leading to hospitalization, OR Necrosis at the injection site, Each with an event onset within the 7-day (Day 1-7) post- vaccination period	≥1
2a*	Any Grade 3 solicited administration site events, with an event onset within the 7-day (Day 1-7) post-vaccination period	≥3/6 or 30%**
2b*	Any Grade 3 solicited systemic events, with an event onset within the 7-day (Day 1-7) post-vaccination period	≥3/6 or 30%**

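### The chills row of Table 23 is graded on narcotic indication and response with no activity criterion, so chills that prevent activity can be recorded below Grade 3 and under-counted in the Grade 3 tables and in holding rule 2b

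*Protocol*

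**What the plan says.** Chills are one of nine solicited systemic events (Protocol Table 22). Table 23 grades them as follows:

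- Grade 1: "Mild sensation of cold; shivering; chattering of teeth"
- Grade 2: "Moderate tremor of the entire body; narcotics indicated"
- Grade 3: "Severe or prolonged, not responsive to narcotics"

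Elsewhere in Table 23, Grade 3 is "Severe: Headache that prevents normal activity", "Severe: Fatigue that prevents normal activity" and "Severe: Myalgia that prevents normal activity". Arthralgia and abdominal pain follow the same pattern.

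The general definition of severe in Section 10.3.5.2, just above the table, is "A type of AE that interrupts usual activities of daily living, or significantly affects clinical status", or an event that may need intensive therapeutic intervention. The section then says that the listed solicited events are assessed by the table.

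The participant records solicited events in an eDiary (Protocol 10.3.3 and 10.3.5.1). SAP 4.2.1.2.1 takes the grade from the eDiary on a modified FDA scale, with Grades 3 and 4 combined, and analyses the maximum over Days 1 to 7.

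These grades are used in two places. Solicited events are part of the primary endpoint, with Grade 3 rows in Protocol 9.4.1 and SAP 4.2.1.1. Holding rule 2b in Protocol Table 12 counts "Any Grade 3 solicited systemic events, with an event onset within the 7-day (Day 1-7) post-vaccination period". Its threshold is 3 of 6 sentinels or 30% of all participants, whichever is met earlier. Protocol 8.3.7.3 applies no formal holding rule to Grade 1 and Grade 2 solicited events.

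**The concern.** Two participants with equally disabling reactions can receive different grades. One kept from normal activity by headache is Grade 3. One kept from normal activity by chills, who has taken no narcotic, has no narcotic response to report, so on the more natural reading the Grade 3 cell does not apply. The protocol makes no provision for narcotics for post-vaccination chills; Section 6.8 only records what is taken.

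Two results are at stake. The Grade 3 chills row of the primary tables may be too low and may discriminate poorly between doses. Also, a participant whose only severe systemic symptom is chills may be missed by rule 2b, which looks at Grade 3 only.

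**Working it through.** **Step 1. The Grade 3 criteria for solicited systemic events, side by side (Tables 22 and 23).**

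| Event | Basis of Grade 3 |
|---|---|
| Headache, fatigue, myalgia, arthralgia, abdominal pain | Prevents activity |
| Vomiting | Prevents activity; outpatient IV hydration also named |
| Fever | Measured temperature |
| Diarrhea | Stool count, stool weight or outpatient IV hydration |
| Chills | Severe or prolonged, with non-response to narcotics |

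Six of the eight other systemic events carry an activity criterion (5 + 1). The two that do not are graded mainly on a measured quantity. Chills are the only systemic event with a narcotic-response condition.

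**Step 2. Narcotics within the same table.** For lymphadenopathy, a solicited administration-site event, needing a narcotic pain reliever is sufficient for Grade 3. For chills, an indication for narcotics is Grade 2. The same fact gives different grades in two rows.

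**Step 3. Two readings of the Grade 3 cell.**

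- Conjunctive: severe or prolonged, and in addition not responsive to narcotics. The Grade 2 cell supports this, because its narcotic clause also reads as an added condition. Activity-preventing chills without narcotic use then fall below Grade 3.
- Loose: the comma separates alternatives, so severe by itself suffices. The same participant can then be Grade 3.

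The protocol does not choose between them.

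**Step 4. The plan's own figures for rules 2a and 2b.** Protocol 8.3.7.3 gives a 90% chance of not holding at 20% true incidence and an 80% chance of holding above 58%, with 6 vaccinated sentinels. With X binomial(6, p),

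P(X ≥ 3) = 1 − [(1−p)^6 + 6p(1−p)^5 + 15p²(1−p)^4].

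- p = 0.20: 1 − (0.2621 + 0.3932 + 0.2458) = 0.099, so not holding is 0.901 (stated 90%).
- p = 0.58: 0.792 (stated 80%).

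Both reproduce. They describe whatever the scale counts as Grade 3.

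**Step 5. Illustration of the effect on rule 2b.** No chills rate is given, so the inputs are assumptions. Suppose the rate that rule 2b sees without chills-only cases is 20%, and chills are the only severe systemic symptom in a further 5% or 10% of vaccinees.

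- p = 0.25: 1 − (0.1780 + 0.3560 + 0.2966) = 0.169.
- p = 0.30: 1 − (0.1176 + 0.3025 + 0.3241) = 0.256.
- If those cases are not counted, p = 0.20 and the probability is 0.099.

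The chance of meeting 3 of 6 falls from 16.9% or 25.6% to 9.9%.

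Part B has no sentinels, so only the 30% criterion can apply there. Assume it is applied to 18 vaccinees in a dose group: 0.30 × 18 = 5.4, so 6 are needed. The chance of at least 6 of 18 is 28.3% at 25% and 46.6% at 30%, against 13.3% at 20%.

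**The case against.** The strongest reply is that the table is ambiguous rather than broken and that other safeguards remain. Several parts of it stand.

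- A reader might infer that the Grade 3 chills rate is zero by construction. The documents do not support that. The loose reading is available, nothing bars narcotics, Section 6.8 has concomitant medication recorded, and the lymphadenopathy row expects that some participants may need a narcotic.
- A reader might infer that shaking chills that keep someone in bed would be Grade 1. That overlooks the word mild at the start of the Grade 1 cell.
- The eDiary text is not in the documents. The participant-facing question on chills may differ from Table 23.
- Table 23 governs solicited events, so the general definition of severe is not a competing rule for them. An activity criterion is also not universal: fever and diarrhea lack one.
- A reader might infer that incapacitated participants vanish from rule 2b. Only those with no other Grade 3 systemic event are lost; Grade 3 fatigue, myalgia, headache or fever still counts.
- The iSRC reviews Grade 1 and 2 data if available and all solicited data at Day 8. It can escalate any safety signal, and rule 1d covers solicited events leading to hospitalization. Chills also stay in the any-grade, Grade 1, Grade 2 and medically attended rows.
- Part B tests only 3 µg and 10 µg. A change taking effect there cannot alter a Part A sentinel decision.

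These points limit the reach and certainty of the finding but do not remove it. The chills row still departs from the other subjective systemic symptoms and from the severity concept of its own section, and two plausible readings of a Grade 3 cell are themselves a source of inconsistent grading.

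**Conclusion.** The point holds as an inconsistency in the grading scale with a possible under-count. On the more natural reading, activity-preventing chills without narcotic use are recorded below Grade 3; on the looser reading they can be Grade 3. Grade 3 chills may therefore be under-counted in the primary tables, and chills-only participants may not count toward rule 2b.

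The textual finding rests only on Table 23 and Section 10.3.5.2. Its practical effect depends on the eDiary following Table 23, which the documents do not show. The fall from 17-26% to 10% rests on assumed rates and on independent participants with a common rate; it illustrates the direction of the effect and is not an estimate for this vaccine. The protocol's stated operating characteristics for rules 2a and 2b are correct for what the scale counts.

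**What to change.** Reconcile the chills row of Table 23 with the definition of severe in Section 10.3.5.2, with the scale used for the other subjective systemic symptoms, and with the treatment of narcotics in the lymphadenopathy row. Because the grades feed a vaccination-hold rule, the wording of each grade is for the sponsor to decide. Use the same wording in the eDiary and in SAP 4.2.1.2.1.

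Check which wording the Part A diaries carried. If it was the narcotics wording, footnote Part A chills grades as not comparable and do not pool chills by grade across Parts A and B. Any-grade chills can still be pooled.

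The cost is one table row, the matching diary text and a SAP footnote. The real downside is loss of Part A to Part B comparability for chills by grade. This matters because the 10 µg group is repeated in Part B to help link the parts (Protocol 4.2), and pooled safety analyses of the common groups are planned (Protocol 9.4.1).

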#### 10.3.5.3. Assessment of causality

- The investigator is obligated to assess the relationship between study intervention and each occurrence of each AE/SAE/AESI. The investigator will use clinical judgment to determine the relationship.
- A *reasonable possibility* of a relationship conveys that there are facts, evidence, and/or arguments to suggest a causal relationship, rather than a relationship cannot be ruled out.
- Alternative causes, such as underlying disease(s), concomitant therapy, and other risk factors, as well as the temporal relationship of the event to study intervention administration, will be considered and investigated.
- For causality assessment, the investigator will also consult the IB and/or product information, for marketed products.
- The investigator must review and provide an assessment of causality for each AE/SAE/AESI and document this in the medical notes There may be situations in which an SAE has occurred and the investigator has minimal information to include in the initial report to GSK. However, it is very important that the investigator always make an assessment of causality for every event before the initial transmission of the SAE data to GSK.
- The investigator may change their opinion of causality in light of follow-up information and send an SAE follow-up report with the updated causality assessment.
- The causality assessment is one of the criteria used when determining regulatory reporting requirements.

